9.3 Planned Analysis

Primary Aim

- To determine the relations between treatment engagement financial incentive amounts offered and likelihood of patient engagement in smoking cessation treatment (defined as setting a TQD and completing the two phone counseling calls (Pre-quit + Week 4).

Primary analysis. The primary outcome measure will be patient engagement in smoking cessation treatment (defined as setting a TQD and the number of completed phone counseling contacts). We will determine the percentage of those in each incentive condition who engage in smoking cessation treatment. We will use logistic regression analyses to contrast the likelihood of engaging in any smoking treatment (vs none) for the three incentive conditions (0 incentive, \$100, and \$50), with the 0 incentive condition being the reference condition in the primary analysis. We will also examine incentive condition effects on the number of scheduled counseling visits completed (0-3 visits) via ordinal logistic regression.

Additional exploratory analyses related to the primary aim. In additional exploratory analyses, we will determine the percentage of all GHC patients who are contacted by the TCOS and offered the Treatment Engagement Incentive. We will separately determine the percentage of those in each incentive condition who agree to set a TQD. We will use logistic regression analyses to contrast the likelihood of engaging in smoking treatment for the three incentive conditions, with (as mentioned above) the 0 incentive condition being the reference condition in the primary analysis, followed by comparison of the \$100 and \$50 conditions both with the reference condition and with one another. The primary analyses will not use covariates. Follow-up analyses will use the patient's home clinic and the patient's TCOS as covariates. Furthermore, using logistic regression, we will examine the relation between incentive condition and use of pharmacotherapy as the outcome (with medication orders and pick-up entered in the EHR and/or billing data).

Exploratory Aims

- Conduct exploratory analyses on the effects of the different incentive engagement amounts on biochemically confirmed point-prevalence 6-month abstinence and determine whether incentive conditions affect abstinence via their effects on smoking treatment engagement (i.e., whether smoking treatment engagement mediates the relations between different engagement incentive conditions and 6-month smoking abstinence).

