Analysis. Logistic regression will be used to determine whether the different incentive levels (\$0, \$100, \$50) produce effects on 6-month, biochemically confirmed point prevalence smoking

abstinence using the strategy described for Primary Aim. Dummy coding will be used to compare: 1) each positive incentive condition with the 0 incentive condition, and 2) the two positive incentive conditions will be compared with one another. The primary analyses will not use covariates. Secondary models will adjust for the patient's home clinic and the patient's TCOS as covariates, Gender, race, cigarettes smoked/day will be added as covariates in later analyses. Mediational analyses will be done using incentive condition as the independent variable, engagement data as mediators (attendance at the initial treatment contact, number of counseling contacts made, or use of smoking medication). The outcome variable will be smoking abstinence at 3 months (self-report only) and 6 months (biochemically confirmed self-report).

- To determine the incremental cost-effectiveness of the different financial engagement incentive amounts with regard to total program costs vs. usual care, net monetary benefit (NMB), cost per quit, and incremental cost-effectiveness ratios (ICERs), with the last determined with regard to cost of additional smoker engaged in treatment and each additional individual who quits smoking.

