9.4 Power

This study is powered to detect a 12 percentage point difference in treatment engagement rates (defined as setting a TQD and completing 2 treatment phone counseling contacts) as a function of incentive amount. We believe that this rate is both feasible and of public health significance. We anticipate that the 0 incentive condition will have an engagement rate of about 15%. Since the rate of smoking treatment engagement is generally only about 5-7% in studies where incentives are not used we believe a 15% rate is conservative. We anticipate increased engagement in the control condition, relative to these earlier studies, because we believe it will be increased by TCOS contact and the opportunity to set a quit date on the contact call. We believe that a 12 percentage point increase above the 15% rate (to 27%) would be of public health significance. A total of 180 participants per group are needed to have power of .80 with alpha = .05 in a two-tailed test. This would translate into a study N = 540 with 180/condition for the comparison of each positive incentive condition vs the control condition. We make no a priori prediction about whether the \$100 incentive condition will increase engagement relative to the \$50 condition, but we certainly believe it will increase engagement relative to the 0 incentive condition. . Therefore, we propose an overall N=540.

While engagement is the principal outcome of this research we nevertheless have determined the effect size (increment in percent abstinent) we would need to have adequate power to detect difference in abstinence rates, as well. We anticipate that the \$0 incentive condition will produce abstinence in 15% of those who contact the TCOS. With n=180/condition, we will have power=.80 to detect at least an 11 percentage point increase in abstinence above the 15% base rate in a 2-tailed test at alpha .05.

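### Section 9.4 claims .80 power for an 11-point rise in abstinence, but its own inputs give about .74, and .80 power needs about 12 points

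*Combined protocol and SAP*

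**What the plan says.** Section 9.4 contains two power statements.

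- **Engagement (primary outcome).** "This study is powered to detect a 12 percentage point difference in treatment engagement rates", from an expected 15% in the zero-incentive condition to 27%. The sample size follows: "A total of 180 participants per group are needed to have power of .80 with alpha = .05 in a two-tailed test". The section continues: "This would translate into a study N = 540 with 180/condition for the comparison of each positive incentive condition vs the control condition".
- **Abstinence (exploratory outcome).** The zero-incentive base rate is again 15%: the "incentive condition will produce abstinence in 15% of those who contact the TCOS". With 180 per condition, two-tailed, alpha .05, "we will have power=.80 to detect at least an 11 percentage point increase in abstinence above the 15% base rate".

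Section 9.3 describes the abstinence analysis as dummy-coded logistic regression that compares "each positive incentive condition with the 0 incentive condition" and then the two positive conditions with each other. On adjustment it says: "The primary analyses will not use covariates". The same section labels the aim as exploratory: "Conduct exploratory analyses on the effects of the different incentive engagement amounts on biochemically confirmed point-prevalence 6-month abstinence".

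**The concern.** The two statements share every input that determines power for a comparison of two proportions: a 15% control rate, 180 per condition, two-tailed alpha of .05 and power of .80. Yet one gives a detectable difference of 12 points and the other 11. No covariate adjustment, different test or different number analysed is given for abstinence that could separate them, so at least one must be wrong.

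At stake is how an abstinence result will be read. Section 9.4 offers the 11-point figure as the effect for which power is adequate. A reader faced with a null abstinence result could take it that the trial had an 80% chance of finding an 11-point effect when the chance was lower. The 6-month abstinence rates also feed the cost-per-quit analysis in section 9.3, so the outcome will be looked at closely even though it is exploratory.

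**Working it through.** **Inputs, all from section 9.4:** p1 = .15; n = 180 per condition, 1:1 for each comparison with the zero-incentive condition; two-sided alpha .05 (z = 1.960); power .80 (z = 0.8416). For engagement p2 = .27; for abstinence p2 = .26. The contrast (each positive condition against zero, no covariates) is from section 9.3.

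**Formula (pooled normal approximation).** With d = p2 − p1 and pbar = (p1 + p2)/2:

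- a = sqrt[2·pbar·(1 − pbar)]
- b = sqrt[p1(1 − p1) + p2(1 − p2)]
- n per condition = [(1.960·a + 0.8416·b)/d]²
- power = Φ[(d·sqrt(n) − 1.960·a)/b]

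**Step 1: reproduce the engagement figure (15% vs 27%).** pbar = .21, a = sqrt(.3318) = .5760, b = sqrt(.3246) = .5697, d = .12.

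- n = [(1.1290 + 0.4795)/.12]² = 179.7, so 180, as the plan states.
- Power at 180 = Φ[(1.6100 − 1.1290)/.5697] = Φ(.844) = .801.

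The 12-point statement reproduces.

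**Step 2: apply the same formula to abstinence (15% vs 26%).** pbar = .205, a = sqrt(.32595) = .5709, b = sqrt(.3199) = .5656, d = .11.

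- Power at 180 = Φ[(1.4758 − 1.1190)/.5656] = Φ(.631) = .736, not .80.
- n for .80 power = [(1.1190 + 0.4760)/.11]² = 210.3, so 211 per condition.

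**Step 3: check that the choice of method does not explain the gap.** Power at n = 180, two-sided .05:

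| Method | 15% vs 26% | 15% vs 27% |
|---|---|---|
| Pooled normal | .736 | .801 |
| Unpooled normal | .742 | .807 |
| Arcsine | .741 | .806 |
| Exact enumeration, Wald logistic contrast | .736 | .801 |
| Exact enumeration, Pearson chi-square | .741 | .806 |

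The fourth row is the uncovaried logistic contrast that section 9.3 plans. Its large-sample approximation gives .725 for 15% vs 26%, and a continuity-corrected chi-square gives .694; both are further from .80. The unpooled and arcsine formulas need 208 per condition for 11 points.

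**Step 4: solve for the increase that gives .80 power at n = 180 and a 15% base.** Pooled 11.99 points, unpooled 11.89, arcsine 11.91. All round to 12.

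**Step 5: look for a reading under which 11 points is right.**

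- *Rounding:* 11.49 points gives only .769.
- *One-sided test:* .829. The text says two-tailed.
- *Both incentive conditions combined (360 vs 180):* .843. The text refers to 180 per condition, and section 9.3 plans separate contrasts.
- *Two-degree-of-freedom overall test:* .797 if the rates are 15/15/26%, that is, if one incentive has no effect at all; .738 if they are 15/26/26%. It is not the pairwise contrast planned.
- *Another base rate:* 11 points at n = 180 gives .80 when the base rate is about 11.3% (pooled), 11.6% (unpooled) or 11.7% (arcsine). The text says 15%.

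**The case against.** The arithmetic itself has no good defence. The phrase about at least 11 points might loosely be read as somewhat more than 11, but its ordinary meaning is that power is .80 at 11. The fair objections concern weight and remedy.

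1. **It matters little.** Abstinence is exploratory, section 9.4 names engagement as the principal outcome, and N=540 is fixed before the abstinence sentence and does not depend on it. The detectable difference is off by about one point. This stands as a limit on the consequence. It does not make the sentence right, and the correction costs almost nothing.
2. **The cause is unknown.** The increment may have been truncated from 11.9, or the base rate may have been meant to be 11 to 12%, with 15% carried over from the engagement calculation. The documents do not settle this. The point stands, and the remedy should let the sponsor correct the base rate or the test if that is where the slip lies.
3. **The 12-point figure assumes complete data.** Section 6.1 speaks of up to 540 participants, and section 9.4 makes no allowance for missing 6-month outcomes. This also stands: 12 points holds only if 180 per condition are analysed.
4. **Reproducing the engagement figure does not endorse the whole sample-size argument.** Agreed. Only its arithmetic was checked here.

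**Conclusion.** The abstinence power statement is wrong as written. With a 15% base rate, 180 analysed per condition and a two-tailed test at .05, power for an 11-point increase is about .74 (.736 to .742 across the five methods tabulated). The type II error there is about 26% (1 − .74), not 20%. The increase detectable with .80 power is about 12 points.

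This rests on the pairwise, uncovaried contrast in section 9.3 and on all 180 per condition contributing an abstinence outcome. It leaves N=540 and the engagement power calculation untouched. It should be corrected, but it does not threaten the primary analysis.

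**What to change.** Replace the last sentence of section 9.4 with, for example: *With 180 participants per condition analysed, power is .80 to detect a 12 percentage point increase in abstinence above a 15% base rate (about .74 for 11 points), two-tailed alpha .05.*

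If the sponsor reached 11 points from a different base rate or test, state that instead, so that base rate, increment, n and power agree.

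The cost is one sentence. Sample size, primary analysis and study procedures stay as they are.

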10.0 Human Subjects Protections and Data Sharing

10.1 Potential Benefits to Subjects and Society

Every participant in the study will be given information about ways to access evidence-based smoking cessation treatment to help them stop smoking and will be given access to that treatment within their healthcare system subject to limits and copays based on insurance coverage. One possible direct personal cost could be from telephone charges for telephone-delivered care such as cessation counseling and care management. Although smokers could access this care outside of the study, we know that only about 1-2% of smokers use a quit line and only about 5% use both medication and counseling. As such, the proposed study will offer all participants the benefit of information about treatment options and a low-barrier method of initiating treatment (i.e., by phone).

The proposed research also has the potential to benefit other smokers by identifying an effective population health incentive intervention that expands the reach of existing treatments with a feasible, cost-effective, and potentially sustainable approach in primary care settings. This work has the potential to accelerate the translation of clinical research on smoking interventions into healthcare practice and thereby reduce morbidity and mortality associated with smoking.

To promote public access to the results of this research, and thus its potential benefits, the study will be registered as a clinical trial at ClinicalTrials.gov, with information about the study purpose, experimental design, outcomes, and analyses available to the general public (with results posted within one year of study closing, as required).

10.2 Potential Risks to subjects

This project poses minimal risk to participants, as it entails only limited data collection solely for research purposes (up to 2 phone assessments with one possible 5-minute visit over 6 months for all enrollees and a modest (non-coercive) incentive to use standard care resources that are already available and consistent with FDA guidelines

The chief risks involved are loss of privacy and breach of confidentiality. Although we will take several steps to protect participant privacy, we cannot guarantee that patients may not experience an invasion of privacy. Some patients may perceive outreach letters from the health system as violating privacy, for example. Likewise, we cannot guarantee the confidentiality of the information collected directly from participants. Although we will not collect sensitive data directly, some data (i.e., substance use disorder diagnoses) may be included in limited data extracted EHR data.

The outreach message and motivational support given to participants in this project are unlikely to induce psychological distress, as they will be positive in tone and will focus on resources available to participants to support their efforts to change. Providing breath samples for carbon monoxide and/or providing saliva or urine for cotinine testing carries minimal risk, as these are minimally invasive procedures.

It is important to note that all patients will have access to evidence-based smoking cessation treatment at no or low cost (through their TCOS or primary care provider, subject to limits and copays based on insurance coverage and/or a quit line that offers evidence-based cessation treatment no cost to callers) and that receiving such treatment is not contingent on consenting to this study. It is also important to note that all patients will have the ability to decline or withdraw from the study and any study activities at any time.

10.3 Risks Minimization Plan.

To protect against breach of confidentiality or violations of privacy, we will ensure that data are stored on secure, encrypted servers at all participating sites, and that transfer of data between clinics and the UW-CTRI research team are conducted via HIPAA-compliant means.

Communication with patients via the MyChart patient portal will likewise be conducted in HIPAA-compliant ways that conform to healthcare system standards. A unique study ID will be used to store all data on individual participants and information linking that study ID to participant identifying information will be maintained by the data manager. Data being used for analysis will be identified with the study ID only. Participant contact information will only be available to study staff having direct contact with participants. Data will be stripped of direct identifiers (limited datasets) or completely de-identified prior to sharing with others outside the IRB-approved research team.

In the course of the study participants may reveal important clinical information to their TCOS (tobacco cessation outreach specialist) regarding a serious health issue or change, the TCOS, who will be an employee of the healthcare system, will be able to communicate directly with the patient's primary care team (e.g., if a patient reports that they are coughing up blood) via the EHR and will advise the patient to seek care from their care team or emergency care, as appropriate.

Routine adverse event assessment will not occur in this study, except in the context of smoking cessation treatment episodes, given the minimal and informational nature of the health system reach interventions and research assessments. Significant adverse events that occur during smoking cessation treatment will be gathered by the TCOS as a part of the patient's standard smoking cessation care. AE's will not be gathered by research staff. If a patient reports a concern AE or health related event to a research staff member, the patient will be encouraged to immediately seek medical attention from the participating healthcare system.

10.4 Risk/Benefit Analysis

This study carries minimal risk. The financial incentives to be deployed pose no risk above and beyond standard treatment and are too small to be coercive. No information about illegal behavior will be collected by research staff or entered into research data bases. The risk of someone's identity becoming known to unauthorized persons is low. This risk is outweighed by the benefits of quitting smoking for any individual, and the benefit to society of having fewer people use tobacco products. This research has the potential to benefit smokers in the future by helping to identify optimal financial incentive levels to promote use of smoking cessation treatments for broader dissemination. Therefore, the potential gain in knowledge regarding engagement incentives associated with the proposed study outweigh the risks of participation.

10.5 Unanticipated Problems or Complications

The Principal Investigator (PI) will be responsible for routinely monitoring study progress. UW-CTRI has a quality assurance monitoring protocol and team in place and will alert the study PI to significant problems that arise. Any data safety concerns will be reported to the PI immediately and addressed. We will report any unanticipated problems to the IRB according to posted guidelines. A full data safety and monitoring plan is included at the end of this protocol.

10.6 Privacy Precautions and Protections

Collection of sensitive information about subjects will be limited to the amount necessary to achieve the aims of the research. Participants will not be asked to disclose any information about illegal behavior.

10.7 Unauthorized Use or Disclosure Precautions and Plan

Participant study data will be collected by TCOS and UW-CTRI research personnel through the UW-ICTR instance of REDCap and will be stored on secure, password protected servers. Data will be accessible only to assigned study staff for their study function; computer workstations will be password-protected, and thus secured from unauthorized use. GHC-SCW healthcare system will transmit identifying information to UW-CTRI via secure, HIPAA compliant means (either a secure FTP site or a secure interface to the EHR).

During the active phase of the study, required patient identifying data will be stored in REDCap and linked to all study data via a study identifier (i.e., to guide randomization, phone calls, and assessments). PHI will be made inaccessible as soon as the study has been completed. Confidentiality of participant data and information will be accomplished by using participant numbers as unique identifiers, allowing us to keep participant data separate from identifying information. At UW-CTRI, data generated through study participation and data obtained from the EHR (with patient consent) and UW-ICTR instance REDCap will be incorporated into a UW-

CTRI analytical database and securely stored under protections and procedures consistent with the guidelines and regulations of the UW School of Medicine and Public Health (UW-SMPH). Outside access is available only via an encrypted connection to the Department of Medicine Citrix server located at the UW Clinical Science Center in Madison. The servers at the UW-CTRI Madison office are physically secured in a locked room. Data backups are created nightly and stored in a locked safe. Significant safeguards have been implemented to protect data including virus and adware protection, firewall, access controls and encryption when appropriate such as wireless and remote access. All UW-CTRI staff members have completed HIPAA and human subjects training and are aware of the sensitivity of study-related data. The study team has a Certificate of Confidentiality from the National Institutes of Health. The UW SMPH has developed school-wide data security policies and procedures. UW-CTRI data security policies and procedures conform to those of the SMPH. UW-CTRI will use the UW-ICTR instance of REDCap that supports audit trails such as access, change logging, and more sophisticated access control for managing and tracking user access privileges. No publications or presentations resulting from this research program will contain any identifying information about individual participants. Following cleaning and verification of data at the conclusion of the study, all research data will be placed in a de-identified data set at UW-CTRI.

Attachment A (revised): Enrollment Flowchart

Population-based Incentive Model to Increase Smoking Cessation Treatment Engagement in Primary Care Study

[figure not shown]
TCOS= Tobacco Cessation Outreach Specialist (GHC Employee)

Attachment A: Enrollment Flowchart

Population-based Incentive Model to Increase Smoking Cessation Treatment Engagement in Primary Care Study

TCOS= Tobacco Cessation Outreach Specialist (GHC Employee)

